8.4.1 Missing Severity Assessment for Adverse Events

If severity is missing for an AE starting prior to the administration of IMP, then a severity of "Mild" will be assigned. If the severity is missing for an AE starting on or after administration of IMP, then a severity of "Severe" will be assigned. The imputed values for severity assessment will be used for incidence summaries, while the actual values will be used in data listings.

8.4.2 Missing Relationship to Investigation Product for Adverse Events

If the relationship to IMP is missing for an AE starting on or after the administration of IMP, a causality of "Related" will be assigned. The imputed values for relationship to IMP will be used for incidence summaries, while the actual values will be presented in data listings.

8.4.3 Missing Seriousness Assessment for Adverse Events

If no information about seriousness is available, the AE will be considered serious. The imputed values for seriousness assessment will be used for incidence summaries, while the actual values will be used in data listings.

8.4.4 Missing/under detection limit Laboratory values

Laboratory values that are "not measurable" or "under detection limit" should not be replaced and should not be included in the summary tables. Quantitative laboratory parameters reported as "< x" or "> y" will be imputed with x/2 and y, respectively, for inclusion in summary statistics. The reported value will be presented in listings.

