# Table 1: Clinical Laboratory Parameters

Clinical Laboratory Parameters	Assessment to be done locally or centrally
Clinical Chemistry	

 
Alanine aminotransferase (ALAT)
 
Aspartate aminotransferase (ASAT)
 
Gamma-glutamyltransferase (γ-GT)
 
Alkaline phosphatase (AP)
 
Bilirubin (direct and indirect if total bilirubin is elevated)
 
Creatinine / creatinine clearance
 
Blood Urea Nitrogen (BUN) or Urea (UREA)
 
Sodium
 
Chloride
 
Potassium
 
Calcium
 
	
 
locally
 

Hematology	

 
Hematocrit
 
Hemoglobin
 
Red blood cells (RBCs)
 
White blood cells (WBC)
 
Differential white blood cells
 
Platelets
 
	
 
locally
 
locally
 
locally
 
locally
 
locally
 
locally
 
locally
 
locally
 

Coagulation	

 
Markers of Coagulation
 
Prothrombin time (PT) / international normalized ratio (INR)
 
Activated partial thromboplastin time (aPTT)
 
Thrombin-antithrombin III complex (TAT)
 
Prothrombin fragments (F1+2)
 
D-Dimer
 
Protein S (PS)
 
Protein C (PC)
 
Antithrombin III (AT III) activity
 
Thrombin Time (TT)
 
Thrombin Generation Test (TGT)
 
	
 
locally
 
locally
 
centrally
 
centrally
 
centrally
 
centrally
 
centrally
 
centrally
 
centrally
 
centrally
 
locally
 

Coagulation Factors (including vWF) 
 
von Willebrand factor (vWF)
 
Factor I (activity of fibrinogen, Clauss assay)
 
Factor I (ROTEM: FIBTEM A10, Maximum clot firmness)
 
Factor II (FII)
 
Factor V (FV)
 
Factor VII (FVII)
 
Factor VIII (FVII)
 
Factor IX (FIX)
 
Factor XI
 
Factor XII (FXIII)
 
	
 
centrally
 
centrally
 
locally
 
centrally
 

Clinical Laboratory Parameters	Assessment to be done locally or centrally
Urinalysis	

 
pH
 
Qualitative for blood
 
White blood cells (WBC)
 
Protein
 
Glucose
 
Ketone bodies
 
Bilirubin
 
Urobilinogen
 
Nitrites
 
	
 
locally
 

Pregnancy Test	
Human chorionic gonadotropin (hCG)	locally
Virus Serology	

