8.4 Missing Data Conventions

In this short study, not many missing values are expected. Therefore, in general, data will not be imputed.

In case there will be at least 10% missing data, these data will be checked at the Blind Data Review Meeting (BDRM) and imputation methods will be considered. It is assumed that these missing data will be at random and an imputation method which is based on the worst case of the respective treatment group will be used as a sensitivity analysis.

For binary endpoints, an observed case analysis (excluding missing data) will be considered to be the primary analysis method and a non-responder analysis (treating missing values as non-responders or the worst case) may be performed as a sensitivity analysis if deemed necessary.

Imputed values will be flagged in listings.

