8.12 Correction of Fibrinogen Level

The fibrinogen level is assessed by FIBTEM A10 test, MCF and Clauss assay at the following visits: screening, prior surgery (baseline), Surgery Day 1 (Prior 1st dose), Surgery Day 1 (Predose)*, Surgery Day 1 (15 minutes after start of first IMP administration), Surgery Day 1 (90 minutes after start of first IMP administration), Surgery Day 1 (end of surgery), and Day 2, Follow-up Visit. (* only applicable in case of repeated intra-operative IMP administration).

Rate of fibrinogen restoring = fibrinogen level at a post-baseline visit / fibrinogen level at baseline*100

If the rate of fibrinogen restoring is \geq 95%, then the fibrinogen level is considered to be successfully corrected at that post-baseline visit for the subject.

The above rate will be calculated for the following visits: Surgery Day 1 (15 minutes after start of first IMP administration), Surgery Day 1 (90 minutes after start of first IMP administration), Surgery Day 1 (End of surgery), and Day 2, Follow-up.

The time to first successful correction of fibrinogen level is classified into the following categories: "Within 15 minutes after IMP start", "Greater than 15 and less than or equal to 90 minutes after IMP start", "Greater than 90 minutes after IMP start" and "Unsuccessful correction".

At every visit, the time point relative to the start time of IMP is calculated in minutes as Collection Time of sample minus Start Time of IMP. Any corrections <15 minutes after IMP start are not considered for classification.

The earliest time point, when the rate is \ge 95%, is the time to first successful correction of fibrinogen level and will be used to categorize the subjects into the respective categories.

Subjects with time to first successful fibrinogen correction on Follow-up Visit Day 2 will be assigned to the category "Greater than 90 minutes after IMP start". If the rate of fibrinogen restoring is < 95% at all the time points, correction of fibrinogen level is reported as "Unsuccessful correction".

A sensitivity analysis adds a time window of ±3 minutes to the category "Within 15 minutes after IMP start", so that time points ≥12 and ≤18 minutes fall into this category. To the category "Greater than 15 and less

than or equal to 90 minutes after IMP start" a time window of +3 minutes is added, so that time points between >18 and ≤93 minutes fall into this category. Corrections >93 minutes are categorized as "Greater than 90 minutes after IMP start".

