12.0 Statistical Methods

All analyses will use SAS[®] version 9.4 or higher.

Subject data listings will be ordered by randomized or actual treatment ('Not randomized' / 'Not treated', 'BT524', 'FFP', 'Cryoprecipitate'), subject number (numerically, ascending) and visit of assessment respectively where applicable. All tables will be presented by treatment arm ('BT524', 'FFP/Cryoprecipitate') and overall. Where applicable tables will also be presented by treatment ('BT524', 'FFP', 'Cryoprecipitate') or by surgery (spinal, abdominal).

Unless otherwise noted, categorical variables will be summarized using number of observations (n), counts and percentages within category. Percentages will be rounded to one decimal place; except 100% will be displayed without any decimal places and percentages will not be displayed for zero counts.

Unless otherwise noted, continuous variables will be summarized using the number of observations (n), arithmetic mean, SD, minimum, Q1, median, Q3 and maximum. The minimum and maximum values will be displayed to the same level of precision as the raw data, the mean, median, Q1 and Q3 to a further decimal place and the SD to two additional decimal places. Unless stated otherwise the calculation of percentages will be based on the total number of subjects in the population of interest. Thus counts of missing observations will be included in the denominator and presented as a separate category.

The significance level will be 2.5% (one-sided), confidence intervals will be 95% (two-sided). All statistical tests (p-values) will be two-sided, unless otherwise stated.

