12.6.3 Laboratory Data

The following clinical laboratory variables will be summarized for the overall population, and separately by type of surgery (spinal and abdominal surgery):

Hematology	Red blood cells (RBC), white blood cells (WBC), platelet count, hemoglobin, hematocrit, neutrophils (absolute and %), lymphocytes (absolute and %), eosinophils (absolute and %) and basophils (absolute and %)
Biochemistry	Aspartate aminotransferase, alanine aminotransferase, creatinine, creatinine clearance (Cockcroft and Gault), blood urea nitrogen (BUN), urea, gamma-glutamyltransferase (γ -GT), alkaline phosphatase (AP), total bilirubin, direct bilirubin, indirect bilirubin, potassium, sodium, calcium and chloride
Urinalysis	pH, blood, WBC, protein, glucose, ketone bodies, nitrite, bilirubin and urobilinogen
Markers of Coagulation	PT, INR, aPTT, TAT, F1+2, D-dimer, PS, PC, AT III, TT and ETP(TGT)
Coagulation factors	FII, FV, FVII, FVIII, FIX, FX, FXI, FXIII and vWF

Note: Protein C (PC) is also referred to as Factor XIV. Direct bilirubin and indirect bilirubin are only assessed in case of an elevated bilirubin value and are thus not generally included in statistical summaries.

Quantitative laboratory parameters reported as "< x" or "y" > will be imputed with x/2 and y, respectively, for inclusion in summary statistics. The reported value will be presented in listings.

Descriptive statistics for clinical laboratory values (in SI units) and changes from baseline at each scheduled assessment visit (as stated in Flowchart of study) with the exception of urinalysis parameters and direct/indirect bilirubin will be presented by treatment and treatment arm.

Laboratory results of all hematology, biochemistry, urinalysis parameters and PT/INR, aPTT will be categorized with respect to the laboratory specific reference ranges as normal/abnormal (i.e., high [H], low [L], where applicable). Abnormal values will be further classified with respect to clinical relevance by the investigator. The results and percentages will be summarized by visit and overall for each treatment and treatment arm.

Shifts from baseline to each post-baseline visit for all laboratory variables (except direct and indirect bilirubin) will be summarized by treatment and treatment arm using number and percentage of subjects.

In addition, a shift summary of hematology for number of subjects with change from normal or not clinical significant to clinical significant will be presented.

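### SAP 8.4.4 drops or keeps an equivalent below-limit laboratory result according to how it is reported, and a known fibrinogen-correction failure can leave the 15-minute denominator

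*SAP*

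**What the plan says.** **Two rules for laboratory results.** SAP 8.4.4 covers results described in words as not measurable or under the detection limit: they "should not be replaced and should not be included in the summary tables". The next sentence covers results reported as less than x or greater than y, which "will be imputed with x/2 and y, respectively, for inclusion in summary statistics". SAP 12.6.3, which governs the laboratory tables, carries only this second rule.

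**Fibrinogen correction.** SAP 8.12 defines "Rate of fibrinogen restoring = fibrinogen level at a post-baseline visit / fibrinogen level at baseline*100", with success at 95% or more. In the time-to-correction analysis a subject is unsuccessful "If the rate of fibrinogen restoring is < 95% at all the time points". Section 8.12 says nothing about below-limit results and does not refer to 8.4.4.

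**Missing data.** For binary endpoints, SAP 8.4 says that "an observed case analysis (excluding missing data) will be considered to be the primary analysis method". A non-responder analysis "may be performed as a sensitivity analysis if deemed necessary". SAP 12.0 has a general rule for percentages, unless stated otherwise: "Thus counts of missing observations will be included in the denominator and presented as a separate category".

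**Status of the fibrinogen tests.** Protocol Table 1 lists "Factor I (ROTEM: FIBTEM A10, Maximum clot firmness" among the clinical laboratory parameters, together with the Clauss assay. SAP 12.6.3 does not list the three assays. SAP 12.5.3.1 summarises them descriptively and tests the correction rate.

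**The concern.** A result under a detection limit x and a result written as less than x carry the same information. Under 8.4.4 the first leaves the tables and the second enters as x/2. Protocol 11.1 has samples analysed in local laboratories at each site or in a central laboratory, and SAP 6.0 plans about 15-20 sites in the EU and Switzerland plus one in the UK, so reporting formats may differ. Two programmers could follow this SAP and produce different tables.

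Below-limit values are the lowest values, so leaving them out is not neutral: it pushes the summary upward.

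The same gap reaches the first-listed secondary efficacy endpoint, the proportion corrected at 15 minutes. A text-only low result gives no ratio, and a subject without a ratio can be treated as missing. That takes out of the denominator a subject whose outcome is effectively known.

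**Working it through.** The plan states no figure on this point, so there is none to reproduce. The steps below check direction and possible size. Detection limits and the share of results below them are not in the documents and are assumed.

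**1. Effect on a mean.** Assume lognormal values with median 1 and coefficient of variation CV, and a fraction f below the limit.

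- s = sqrt(ln(1 + CV²)); true mean m = exp(s²/2); limit x = exp(s·z_f), where z_f is the normal f-quantile.
- Part of the mean above the limit: U = m·Φ(s − z_f).
- Mean after dropping: U/(1 − f). Mean after imputing x/2: U + f·x/2.

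Example with CV 0.3 and f = 10%: s = 0.294, m = 1.044, x = 0.687, U = 0.984. Dropping gives 0.984/0.9 = 1.093, which is 4.7% too high. Imputing gives 0.984 + 0.1 × 0.343 = 1.018, which is 2.5% too low.

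| Share below limit | Drop, CV 0.3 | x/2, CV 0.3 | Drop, CV 0.6 | x/2, CV 0.6 |
|---|---|---|---|---|
| 2% | +1.1% | −0.4% | +1.6% | −0.2% |
| 5% | +2.5% | −1.2% | +3.8% | −0.5% |
| 10% | +4.7% | −2.5% | +7.4% | −1.2% |
| 20% | +9.0% | −5.3% | +14.8% | −2.8% |

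Dropping raises the mean in every case. Imputing x/2 is not unbiased, but its error is smaller in every case.

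**2. Is a below-limit fibrinogen result a known failure?** The true rate is below x/b, where b is the baseline value. Failure is certain if x/b ≤ 0.95, that is b ≥ x/0.95. Assume a limit of 2 to 5 mm. Take 9-25 mm as the baseline range; this is the reference range that Protocol 9.1.2.2 gives for MCF, used here as a stand-in for FIBTEM A10. Then x/b runs from 2/25 = 8% to 5/9 = 56%, well under 95%. With x = 5 mm, any baseline of at least 5/0.95 = 5.3 mm makes failure certain. No imputed value is needed to classify the subject.

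**3. Effect on the correction rate.** Take 100 subjects per arm (the planned evaluable number), r corrected, and k below-limit failures dropped. The rate moves from r/100 to r/(100 − k).

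| r | k = 1 | k = 2 | k = 5 | k = 10 |
|---|---|---|---|---|
| 40 | 40.4% | 40.8% | 42.1% | 44.4% |
| 60 | 60.6% | 61.2% | 63.2% | 66.7% |
| 80 | 80.8% | 81.6% | 84.2% | 88.9% |

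With 60 corrected in both arms and k = 5 in one arm only, a true difference of zero becomes 63.2 − 60.0 = 3.2 percentage points.

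**4. How the sections combine at 15 minutes.** A text-only low result is not replaced (8.4.4), so the ratio in 8.12 cannot be formed. The subject is then missing, and 8.4 excludes missing data in the primary handling of binary endpoints. The general denominator rule in 12.0 applies only where nothing else is stated, and 8.4 states something else. If the same result had been written as less than x, and x/2 were carried into 8.12, the subject would count as a failure.

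**The case against.** **Two formats, not a contradiction.** The two sentences of 8.4.4 can be read as covering two reporting formats: text with no number attached, and reports that carry a limit. This stands. A reader might infer that the SAP contradicts itself outright; the text supports only an unresolved overlap. The overlap still lets format decide whether equivalent results are used.

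**Not every dropped value is low.** For PT, aPTT and TT, an unmeasurable result can mean a clotting time too long to record, or a technical failure. Dropping a very long time biases the mean downward. A reader might infer that all coagulation means are inflated; that holds only for results below a lower limit.

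**The correction endpoint is not mentioned in 8.4.4.** The exclusion there is limited to summary tables, and 8.12 has its own derivation. A reader might infer that the SAP orders low fibrinogen results out of the correction analysis. It does not. The route in step 4 is an inference from Protocol Table 1 and SAP 8.4, 8.4.4 and 8.12 taken together. It is open because 8.12 is silent.

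**Safeguards exist.** Reported values stay in the listings. SAP 8.12 repeats the correction analysis with MCF and Clauss. Later time points can still classify a subject in the time-to-correction analysis. SAP 8.4 allows a non-responder analysis, and considers worst-case imputation as a sensitivity analysis when at least 10% of data are missing. These help only in part: the non-responder analysis is optional, the 10% trigger may not be reached, MCF and Clauss share the gap, and later time points do not repair the 15-minute proportion. A subject with no ratio at 15 minutes and failure afterwards is also not clearly below 95% at every time point.

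**Low consequence.** SAP 12.5.2 calls the secondary analyses exploratory. This stands.

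**Conclusion.** The point holds as a minor defect in data handling. Equivalent below-limit results are dropped or set to x/2 according to reporting format, 12.6.3 carries only one of the two rules, and dropping low results biases summaries upward. A subject with an unmeasurably low FIBTEM A10, MCF or Clauss result at 15 minutes can leave the denominator of the correction rate, although normally a known failure.

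The size cannot be determined, because the documents give neither detection limits nor expected frequencies. The ranges above (+1.1% to +14.8% on a mean; 0.4 to 8.9 percentage points on a correction rate) rest on the assumed lognormal shape and on assumed shares of 2% to 20% and counts of 1 to 10 per 100. Nothing in the documents indicates an imbalance between arms, so an effect on the treatment comparison is conditional. The primary endpoint, intra-operative blood loss, and the sample size are not affected.

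**What to change.** - **SAP 8.4.4 and 12.6.3:** use one rule in both places. Every below-limit result enters summaries as x/2 whatever its reporting format, with x the assay limit supplied by the laboratory, and is flagged. Above-range results enter as y. Only results missing for technical reasons are excluded.
- **SAP 8.12:** state that a below-limit post-dose fibrinogen result counts as not corrected at that time point, for FIBTEM A10, MCF and Clauss alike. An explicit sentence is safer than carrying x/2 into the ratio, because a below-limit baseline and post-dose result would then give (x/2)/(x/2) = 100% and count as corrected.
- **SAP 8.4 and 12.0:** say which denominator applies to the correction rate, so that the observed-case rule and the general percentage rule agree.

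The cost is a few sentences of SAP text, a request to the laboratories for their assay limits, a way to tell below-limit results from technical failures, and a small change to the derivation, all before database lock. No new subject data are needed.

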8.5 Handling of partial dates and missing/incomplete times

For prior or concomitant medications, incomplete (i.e., partially missing) start date and/or stop date will be imputed. When the start date and the stop date are both incomplete for a subject, impute the start date first.

For AEs, incomplete (i.e., partially missing) start dates and times and/or incomplete stop dates and times will be imputed.

For transfusion products, incomplete start and/or stop times will be imputed.

Imputation rules for incomplete dates for prior or concomitant medications, incomplete dates and times for AEs, and incomplete times for transfusion products are described in sections 8.5.1 and 8.5.2.

Imputed dates will be used for all further derivations (e.g., treatment-emergent adverse event [TEAE] definition, classification of medications as prior or concomitant, and study day calculation). Imputed dates will also be used and flagged in listings.

Imputed dates will be indicated in the listings by using 'D' if only day is imputed, and 'M' if day and month are imputed, Imputed times will be indicated in listings by using 'm' if only minutes are imputed and 'h' if minutes and hours are imputed. It is not expected that dates for any other parameter are missing. Should any other dates be missing or partially missing, then statistical programming will place a warning in the log file and inform the statistical lead should these dates be required for derivations.

8.5.1 Incomplete Start Date and Time

The following rules will be applied to impute the missing numerical fields. If the stop date is complete and the imputed start date is after the stop date, then the start date will be imputed using the stop date.

Missing Day and Month

- If the year of the incomplete start date is the same as the year of the date of the first dose of IMP, then the day and month of the date of the first dose of IMP will be assigned to the missing fields.
- If the year of the incomplete start date is before the year of the date of the first dose of IMP, then December 31 will be assigned to the missing fields.
- If the year of the incomplete start date is after the year of the date of the first dose of IMP, then 01
 January will be assigned to the missing fields.
- If the subject was not treated (no IMP start date), then 01 January will be assigned to the missing fields.

Missing Month Only

• The day will be treated as missing and both month and day will be replaced according to the above procedure.

Missing Day Only

- If the month and year of the incomplete start date are the same as the month and year of the date of the first dose of IMP, then the day of the date of the first dose of IMP will be assigned to the missing day.
- If either the year is before the year of the date of the first dose of IMP or if both years are the same but the month is before the month of the date of the first dose of IMP, then the last day of the month will be assigned to the missing day.
- If either the year is after the year of the date of the first dose of IMP or if both years are the same but the month is after the month of the date of the first dose of IMP, then the first day of the month will be assigned to the missing day.
- If the subject was not treated (no IMP start date), then the first of the month will be assigned to the missing field.

Missing/Incomplete Time

- If the time is missing and the date is complete and is the same as the date of the first dose of IMP, or the date is imputed to be this date, then the time will be set to the time of the first dose of IMP. Otherwise, missing times will be imputed as 00:00.
- If the minutes are given but the hour is not, then the time will be regarded as completely missing and handled as above.
- If the hour is given but the minutes are not, then if the hour is the same as the hour of the first dose of IMP, then the minutes of that dose of IMP will be assigned to the missing fields. Otherwise 00 will be assigned to the missing minutes.
- If the subject was not treated (no IMP start date), then missing times will be imputed as 00:00.

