8.5.2 Incomplete Stop Date and Time

The following rules will be applied to impute the missing numerical fields. If the imputed stop date is before the start date (imputed or non-imputed start date), then the imputed stop date will be equal to the start date.

Missing Day and Month

- If the year of the incomplete stop date is the same as the year of the date of the study discontinuation/completion, the stop day and month will be set to the maximum of the date of study discontinuation/completion, as appropriate, or the date equivalent to 35 days after the last dose of IMP.
- If the year of the incomplete stop date is before the year of the date of study discontinuation/ completion, as appropriate, or the date equivalent to 35 days after the last dose of IMP, the day and month will be set to 31 December.
- If the year of the incomplete stop date is after the year of the date of study discontinuation/ completion, as appropriate, or the date equivalent to 35 days after the last dose of IMP, the day and month will be set to 01 January.

Missing Month Only

• The stop day will be treated as missing and both month and day will be replaced according to the above procedure.

Missing Day Only

• The stop day will be set to the last day of the month.

Totally Missing Stop Date

• The concomitant medication will be considered ongoing.

Missing /Incomplete Time

- If the time is missing, it will be imputed as 23:59.
- If the minutes are given, but not the hour, then the time will be regarded as completely missing and handled as above.
- If hours are given, but minutes are not, minutes will be imputed with 59.

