12.3.4 Transfusion Products

The type of transfusion products includes autologous blood transfusion/cell salvage, allogenic platelet concentrates, allogeneic RBCs, allogeneic FFP, cryoprecipitate and other.

The number and percentage of subjects, using any transfusion products will be summarized by treatment and treatment arm for the SAF. This will be repeated by surgery type. The number and percentage of subjects will also be presented for each type of transfusion product. The volume (mL) of administration for each type of transfusion product will be summarized as well. This will also be repeated by surgery type. These summaries will also be performed separately for RBCs taken before start of first IMP (SAF) and for each type of transfusion product after start of first IMP (SAF). Transfusion products will be listed for the All Subjects Enrolled Set.

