12.6.1 Adverse Events

Adverse events will be coded using the most updated version of the MedDRA® dictionary.

Adverse events occurring during or after the administration of study medication are TEAEs. If a partially missing AE start date is imputed, the imputed date will be used to assess if the AE is treatment emergent. If AE start date is completely missing and AE end date/time is after IMP start date/time or if it is completely missing, then it is a TEAE. All other AEs are regarded non-treatment emergent.

The search criteria for the adverse events of special interest are specified in the table below:

AESI	Search Criteria
Thrombosis or TEE	SMQ: Embolic and thrombotic events (narrow)
Relevant bleeding complication	All AESIs ticked as AESI, but not falling under categories "Thrombosis or TEE" or "Suspicion of transmission of infective agents (viral safety)"
Suspicion of transmission of infective agents (viral safety)	Preferred terms: "transmission of infectious agent via product" and "suspected transmission of infectious agent via product"

Adverse events related to Hypersensitivity/anaphylactic reactions/anaphylactic shock will be selected by using the following criteria: SMQ: Hypersensitivity, (narrow), Anaphylactic reaction (narrow), and Anaphylactic shock conditions (narrow).

Adverse events related to bleeding related ischaemic events will be selected by using the following criteria: SMQ: Ischaemic heart disease: Myocardial infarction (narrow), Other ischaemic heart disease (narrow); Ischaemic colitis (broad); Ischaemic central nervous system vascular conditions (narrow); Embolic and thrombotic events, arterial (narrow); Embolic and thrombotic events, venous (narrow); PT: Peripheral ischaemia; Ischaemia; Gastric ischaemia; Hepatic ischaemia; Ischaemic contracture of the left ventricle; Dry gangrene; Ischaemic gastritis; Ischaemic limb pain; Necrosis ischaemic; Spleen ischaemia; Uterine ischaemia.

If a serious adverse event (SAE) occurs in a subject after the period of observation, i.e., after the last study visit, and is considered by the investigator to be related to the study medication, this should still be recorded as a SAE. If the eCRF has been closed for the subject, the investigator should contact the sponsor to determine how to report the SAE.

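### SAP 8.5.1 places untimed surgery-day transfusions and adverse events at the first IMP dose and checks start against stop by date only, so some same-day records are misclassified (minor)

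*SAP*

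**What the plan says.** SAP 8.5 sets the scope. AE start and stop dates and times are completed by rule, and the same is said of transfusions: "For transfusion products, incomplete start and/or stop times will be imputed".

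SAP 8.5.1 gives the start-time rule. Its trigger is "If the time is missing and the date is complete and is the same as the date of the first dose of IMP" (or a date imputed to that day); its result is "then the time will be set to the time of the first dose of IMP. Otherwise, missing times will be imputed as 00:00". The section then qualifies this:
- Minutes known without the hour count as fully missing.
- Hour known without minutes: the dose minutes are used if the hour is the dose hour, otherwise 00.
- Untreated subjects get 00:00.

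The consistency check in 8.5.1 is worded in dates: with a complete stop date, if "the imputed start date is after the stop date, then the start date will be imputed using the stop date". The matching check in 8.5.2 is also by date, and for stop times that section says: "If the time is missing, it will be imputed as 23:59".

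These times are used in four places:
- SAP 12.5.3.2 and 12.5.3.3 count transfusion products and red blood cells (RBCs) from the start of first IMP to the end of surgery.
- SAP 12.3.4 has a separate table of RBCs given before first IMP.
- SAP 12.6.1 defines treatment emergence: "Adverse events occurring during or after the administration of study medication are TEAEs". Where the AE start date is wholly missing, it compares the AE's end date and time with the IMP start.

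**The concern.** Setting an unknown onset to the dose time is a familiar device for AEs, because it errs towards calling the event treatment-emergent. Transfusions have no such safe side. The periods before the dose, from dose to last suture, and after surgery on Day 1 all fall on one date, and only the clock time separates them. A rule that gives all three the same clock time, with a check that sees only dates, cannot tell them apart.

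At stake are the two transfusion endpoints, the pre-IMP RBC table, the summary in 12.5.3.2 of subjects who avoided all transfusion after IMP, and the treatment-emergent status of some AEs. The rule can also override recorded information: a stop time before the dose shows that the event was over, yet its start is placed after that stop.

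**Working it through.** The plan states no figure on this point, so there is none to reproduce. The check applies 8.5.1 as written to test records. The clock times are assumptions chosen to exercise the rule, not trial data: surgery 08:00 to 15:00, first IMP 09:30. For every record the start and stop dates are equal, so the date check never fires.

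| Record (true times) | Missing | Imputed start | Recorded stop | True class | Class by the rule |
|---|---|---|---|---|---|
| A. RBC 08:20–08:50 | start time | 09:30 | 08:50 | pre-dose | on the edge |
| B. RBC 12:00–12:30 | start time | 09:30 | 12:30 | in window | on the edge |
| C. RBC 18:00–18:40 | start time | 09:30 | 18:40 | post-operative | on the edge |
| D. RBC 08:20–08:50 | minutes only | 08:00 | 08:50 | pre-dose | pre-dose |
| E. RBC 18:20–18:50 | minutes only | 18:00 | 18:50 | post-operative | post-operative |
| F. RBC 09:10–09:20 | minutes only | 09:30 | 09:20 | pre-dose | on the edge |
| G. AE 07:00–07:40 | start time | 09:30 | 07:40 | not treatment-emergent | treatment-emergent |
| H. AE 20:00–23:00 | start time | 09:30 | 23:00 | treatment-emergent | treatment-emergent |

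**Impossible records.** Imputed start minus recorded stop is 09:30 − 08:50 = 40 minutes for A, 09:30 − 09:20 = 10 minutes for F, and 09:30 − 07:40 = 110 minutes for G. Each starts after it ended.

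**The edge.** Among A, B and C, one unit (B) is truly in the window. If a start equal to the dose time counts as inside, the rule counts all three. If it does not, the rule counts none. Neither reading gives one. Under either reading A is absent from the pre-IMP RBC table, because its start is no longer before the dose.

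**Where the rule works.** D and E are classified correctly, so a known hour other than the dose hour is safe. For H only the time to onset is wrong (0 instead of 20:00 − 09:30 = 10.5 hours).

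**Conflict within the SAP.** Take G twice. If its start date is wholly missing, 12.6.1 sees an end before IMP and classes it as not treatment-emergent. If its start date is known and only the time is missing, 8.5.1 supplies the dose time and the event is treatment-emergent. The record with more information gets the worse answer.

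**Both times missing.** A unit with neither time runs from the dose time to 23:59. The imputed stop carries no information, so a stop-time check cannot help and only the surgical phase can.

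**Scale.** With an inclusive edge, the error in an arm's mean equals its mean number of untimed same-day units that truly lie outside the window. With an exclusive edge it equals minus the mean number that truly lie inside. In an arm of 100 subjects, one such unit moves the mean by 1/100 = 0.01 units. How many such units there are is not in the documents.

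**The case against.** The strongest reply is that this concerns few records and low-stakes analyses. SAP 8.4 expects few missing values. SAP 12.5.2 calls the secondary analyses exploratory, and 12.5.3.2 only describes overall transfusion use. For AEs of unknown onset on the dosing day, counting them as treatment-emergent guards against under-reporting. Imputed times are flagged in listings, and validation checks, source data verification and dry-run review could catch a stop before a start. All of this limits the size. None of it changes the rule, which still gives a wrong class where the recorded data show the right one.

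Several stronger readings are tempting but not supported:
- *Every missing surgery-day start time goes to the dose.* No. This holds, in treated subjects, for fully missing times (including minutes without the hour) and for the dose hour with minutes missing.
- *A barred pre-dose platelet or plasma unit is moved into a permitted period, which alters the per-protocol set.* No. Protocol 6.10 bars such products during the first IMP administration as well as before it, so a start at the dose time is still in the barred period. Deviations also pass through monitoring, data checks and the blind data review meeting (SAP 12.2).
- *The bias differs by arm because cryoprecipitate is thawed after randomisation.* A longer wait is plausible from Protocol 6.6, but no document links missing times or pre-dose RBCs to arm.
- *The endpoint is inflated by a large percentage.* Such a figure depends wholly on how many untimed units one puts into an example.

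**Conclusion.** The point holds in a limited form and is minor. As written, 8.5.1 misclassifies an AE whose recorded stop precedes the first dose, and it cannot classify a same-day transfusion without a usable start time. The unstated edge rule decides whether out-of-window units are counted or true intra-operative units are lost.

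The mechanism follows from the SAP text alone. The direction for transfusions depends on the edge reading. Pairing tables for before and after first IMP makes the inclusive reading the more natural one, but the SAP does not say so. The size is unknown and probably small, because no rate of missing times is given. The primary endpoint is measured blood loss and does not use these times.

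**What to change.** Amend SAP 8.5.1 as follows:
1. Compare date and time. If a recorded (not imputed) stop date/time is before the imputed start, set the start to the stop. An event that ended before first IMP is then pre-dose and not treatment-emergent, in line with 12.6.1.
2. For transfusion products with a missing start time, drop the IMP-start rule. Assign the period (pre-dose, post-dose intra-operative or post-operative) from the recorded stop time where that settles it, as a stop before the dose does. Otherwise use the recorded visit or phase, if the eCRF holds it. The visit schedule in Protocol 7.1 documents transfusions by phase, but whether the eCRF stores this must be confirmed.
3. State whether a start equal to the IMP start is inside the window. Report units that cannot be assigned both included and excluded, as a sensitivity count.

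The cost is SAP wording and a few lines of programming. A few units may stay unassigned. Reporting the count both ways shows their effect, whereas leaving them out altogether would bias the count downwards.
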